8.1. Policies to decrease adverse events

1. Transvaginal cervical length: Sonographers who will be performing screening transvaginal ultrasounds at all sites will be certified through CLEAR or equivalent before the start of the study.
2. Pelvic exam: Pelvic exam will be performed by trained obstetrician & gynecologist or nurse practitioner.
3. Cervical cerclage placements: Surgical procedure will be performed by trained obstetrician & gynecologist in this surgical technique
4. Anesthesia: will be provided by trained anesthesiologist in the operating room

8.2 Definitions

Unanticipated Problems Involving Risk to Subjects or Others

Any incident, experience, or outcome that meets all of the following criteria:

- Unexpected in nature, severity, or frequency (i.e. not described in study-related documents such as the IRB-approved protocol or consent form, the investigators brochure, etc)
- Related or possibly related to participation in the research (i.e. possibly related means there is a reasonable possibility that the incident experience, or outcome may have been caused by the procedures involved in the research)
- Suggests that the research places subjects or others at greater risk of harm (including physical, psychological, economic, or social harm).

Unanticipated Adverse Surgical procedure Effect

An Unanticipated Surgical procedure Effect is any serious adverse effect on health or safety, or any life-threatening problem or death caused by, or associated with a surgical procedure, if that effect, problem, or death was not previously identified in nature, severity, or degree of incidence in the investigational plan or application (including a supplementary plan or application), or any other unanticipated serious problem associated with a that relates to the rights, safety, or welfare of subjects.

Serious injury

Any injury or illness that is any one of the following:

- Life-threatening

- Results in permanent impairment of a body function or permanent damage to body structure
- Necessitates medical or surgical intervention to preclude permanent impairment of a body function or permanent damage to a body structure

Adverse Event

An adverse event (AE) is any symptom, sign, illness or experience that develops or worsens in severity during the course of the study. Intercurrent illnesses or injuries should be regarded as adverse events. Abnormal results of diagnostic procedures are considered to be adverse events if the abnormality:

1. Results in study withdrawal
2. Is associated with a serious adverse effect related to the surgical procedure
3. Is associated with clinical signs or symptoms
4. Leads to additional treatment or to further diagnostic tests
5. Is considered by the investigator to be of clinical significance

What will be monitored:

Stopping rules: Any unanticipated effects and all adverse effects resulting in research subject death or injury will be reported to the PI immediately, no later than 10 days after the event and will include:

1. Maternal sepsis with admission to ICU attributable to the cerclage placement
2. Maternal death attributable to the cerclage placement
3. Maternal bleeding requiring blood transfusion attributable to cerclage placement
4. Fetal and/or neonatal death or injury attributable to the cerclage placement

Frequency of monitoring reports: after approximately 50% of the subjects have delivered

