8.4 Reporting of Adverse Effects and Unanticipated Problems

8.4.1 Investigator reporting: Notifying the principal investigator

Principal investigator contact information for reporting purposes

Report adverse effects by phone and facsimile to:

[name]
Email: [contact]
[contact]
[contact]

Adverse Effects

Any adverse effect that results in serious injury or death, and any type of unanticipated adverse effect, regardless of seriousness or severity, must be reported to the principal investigator by telephone within 24 hours of the event.

Within the following 48 hours, the principal investigator shall provide further information, as applicable, on the unanticipated adverse event or the unanticipated problem in the form of a written narrative. This should include a copy of the completed Unanticipated Problem form, and any other diagnostic information that will assist the understanding of the event. Significant new information on ongoing unanticipated adverse effects shall be provided promptly to the principal investigator.

Deviations from the study protocol

Deviations from the protocol must receive both principal investigator and the investigator's IRB approval before they are initiated. Any protocol deviations initiated without principal investigator and the investigator's IRB approval that may affect the scientific soundness of the study, or affect the rights,

safety, or welfare of study subjects, must be reported to the Principal investigator and to the investigator's IRB as soon as a possible, but no later than 5 working days of the protocol deviation.

Withdrawal of IRB approval

An investigator shall report to the principal investigator a withdrawal of approval by the investigator's reviewing IRB as soon as a possible, but no later than 5 working days of the IRB notification of withdrawal of approval.

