8.4.2 Investigator reporting: Notifying the IRB

Adverse Effects

All unanticipated effects and all adverse effects resulting in research subject death or injury reported by the investigator to the study Principal investigator must also be reported to the investigator's local IRB in accordance with their reporting requirements, though no later than 10 working days.

Protocol Deviations

Any protocol deviations initiated without principal investigator and/or the investigator's IRB approval that may affect the scientific soundness of the study, or affect the rights, safety, or welfare of study subjects, must be reported to the Principal investigator and to the investigator's IRB as soon as a possible, but no later than 5 working days of the protocol deviation.

Any adverse event that occurs any time during or after the research study, which in the opinion of the principal investigator is:

- Unexpected (An event is "unexpected" when its specificity and severity are not accurately reflected in the protocol-related documents, such as the IRB-approved research protocol, any applicable investigator brochure, and the current IRB-approved informed consent document

AND

- Related to the research procedures (An event is "related to the research procedures" if in the opinion of the principal investigator, the event was more likely than not to be caused by the research procedures.)

The above is required regardless of whether the event is serious or non-serious, on-site or off-site

Adverse Effects

All unanticipated effects and all adverse effects resulting in research subject death or injury must be reported to the investigator's local IRB in accordance with their reporting requirements, though no later than 10 working days.

Protocol Deviations

Any protocol deviations initiated without principal investigator and/or IRB approval that may affect the scientific soundness of the study, or affect the rights, safety, or welfare of study subjects, must be reported to the investigator's IRB as soon as a possible, but no later than 5 working days of the protocol deviation.

Reporting Process

Report unanticipated problems as defined above to the IRB office as a written report of the event (including a description of the event with information regarding its fulfillment of the above criteria, follow-up/resolution and need for revision to consent form and/or other study documentation).

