Copies of each report and documentation of IRB notification and receipt will be kept in the Clinical Investigator's study file.

Other Reportable events:

For clinical trials, the following events are also reportable to the IRB:

- Any adverse event that would cause the principal investigator to modify the protocol or informed consent form, or would prompt other action by the IRB to assure protection of human subjects.
- Information that indicates a change to the risks or potential benefits of the research, in terms of severity or frequency. For example:
 - An interim analysis indicates that participants have a lower rate of response to treatment than initially expected.
 - Safety monitoring indicates that a particular side effect is more severe, or more frequent than initially expected.
 - A paper is published from another study that shows that an arm of your research study is of no therapeutic value.
- Breach of confidentiality
- Change to the protocol taken without prior IRB review to eliminate apparent immediate hazard to a research participant.
- Incarceration of a participant when the research was not previously approved under Subpart C and the investigator believes it is in the best interest of the subject to remain on the study.
- Complaint of a participant when the complaint indicates unexpected risks or the complaint cannot be resolved by the research team.
- Protocol violation (meaning an accidental or unintentional deviation from the IRB approved protocol) that in the opinion of the investigator placed one or more participants at increased risk, or affects the rights or welfare of subjects.

Unanticipated Adverse Effects

Evaluation

The principal investigator shall immediately evaluate each Unanticipated Adverse Effect. Such evaluations shall be reported to the IRB office, and participating investigators, within 10 working days after the principal investigator first receives notice of the effect.

Unreasonable risk to subjects

After evaluating an Unanticipated Adverse Effect, if the principal investigator determines the effect presents an unreasonable risk to subjects, the principal investigator shall terminate the study or parts of the study presenting that risk as soon as possible. Study termination shall occur no later than 5 working days after the principal investigator makes this determination and not later than 15 working days after the principal investigator first received notice of the effect.

Withdrawal of IRB approval

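### The Stopping rules paragraph triggers only a report: no visible text pauses randomisation or requires DSMB review after a catastrophic maternal event, and its 10-day limit conflicts with the 24 hours in section 8.4.1

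*Combined protocol and SAP*

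**What the plan says.** Section 8.2 (Definitions) has a paragraph labelled as stopping rules. Its operative words concern reporting: "Stopping rules: Any unanticipated effects and all adverse effects resulting in research subject death or injury will be reported to the PI immediately". With the time limit, the events "will be reported to the PI immediately, no later than 10 days after the event and will include" four items. Two are catastrophic for the mother: "Maternal sepsis with admission to ICU attributable to the cerclage placement" and "Maternal death attributable to the cerclage placement". The other two are bleeding that needs transfusion, and fetal or neonatal death or injury, each attributable to cerclage. The only other content is the timing of monitoring reports, once about half of the subjects have delivered.

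Other sections bear on the same events:

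- **Section 8.4.1:** an effect causing serious injury or death, or any unanticipated effect, "must be reported to the principal investigator by telephone within 24 hours of the event".
- **Section 8.4.2, IRB reporting:** effects resulting in death or injury go to the local IRB "in accordance with their reporting requirements, though no later than 10 working days". Also reportable are the finding that "Safety monitoring indicates that a particular side effect is more severe, or more frequent than initially expected" and any "Change to the protocol taken without prior IRB review to eliminate apparent immediate hazard to a research participant".
- **Section 8.4.2, evaluation and termination:** the PI must evaluate each unanticipated adverse effect at once. If the PI judges it an unreasonable risk, the study or the affected part must end as soon as possible, within 5 working days of that judgement and 15 working days of first notice.
- **Sections 8.4.1 and 8.4.2:** both provide for withdrawal of IRB approval.
- **Section 8.5:** the PI oversees safety, assesses adverse events regularly and sets up a site-level safety-monitoring plan.
- **Section 8.5.1:** an independent DSMB reviews safety data once, at about 50% delivered. Its head is told of unanticipated problems.

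**The concern.** A reader who looks under the stopping label for what happens after a maternal death finds whom to tell and by when, but no action. If the text is followed exactly, women can still be randomised to cerclage while a cerclage-attributed death or ICU sepsis is being evaluated. An independent DSMB exists, yet nothing visible requires it to look at that event. Its one scheduled review depends on the number of deliveries, so an event after that review has no scheduled DSMB look at all.

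The two time limits for telling the PI also disagree. A site that reads only section 8.2 could take 10 days to report a death that section 8.4.1 wants telephoned within 24 hours.

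**Working it through.** **Text check.** For each safeguard, I asked whether it holds randomisation while the event is evaluated, and whether it obliges the DSMB to review the event.

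- Section 8.2, stopping paragraph: neither. It requires a report to the PI.
- Section 8.4.1, 24-hour call: neither. It requires a report to the PI.
- Section 8.4.2, IRB reporting: neither. The IRB may act, or withdraw approval, once told.
- Section 8.4.2, immediate-hazard item: neither. It makes a change already taken reportable, so it presupposes that the PI may act but does not require it.
- Section 8.4.2, evaluation and termination: no hold during evaluation and no DSMB role. It is worded for unanticipated effects and depends on the PI's judgement.
- Section 8.5: no such action is stated. The site plan itself is not reproduced in the document.
- Section 8.5.1: notice to the DSMB head of unanticipated problems, but no required review or recommendation on a single event.

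**Size.** The plan gives no figure on this point, so there is none to reproduce. The inputs are 52 women, 26 per arm (section 7.1), 1:1 allocation (section 7) and 3 years of enrolment (Study Summary). Steady accrual is assumed.

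1. Accrual: 52 / 156 weeks = 0.333 per week, or one woman per 3 weeks. Cerclage arm: 0.333 / 2 = 0.167 per week.
2. Outer limit for termination: 15 working days = 3 weeks = 21 days from notice to the PI. Randomised: 3 × 0.333 = 1.0. To cerclage: 3 × 0.167 = 0.50. Chance of at least one (Poisson): 1 − exp(−0.50) = 0.39.
3. Counted from the event, with the PI told within 24 hours: 22 days, 22/7 × 0.1667 = 0.52, and 1 − exp(−0.524) = 0.41.
4. Counted from the event, with the PI told at the 10-day limit: 31 days, 31/7 × 0.1667 = 0.74, and 1 − exp(−0.738) = 0.52.
5. Chance of at least one catastrophic maternal event among 26 cerclages, 1 − (1 − p)^26. The documents give no rate, so p is assumed: 0.1% gives 0.026, 0.5% gives 0.122 and 1% gives 0.230.
6. Chance that an event occurs and another woman is allocated to cerclage within the 21 days (step 5 × 0.393): 0.010, 0.048 and 0.090, or about 1% to 9%.

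Step 6 treats the two parts as independent and lets the PI use the whole limit. An event near the end of enrolment would leave fewer women to follow. The figures are therefore outer values for the assumed rates.

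**Cost of a pause.** A 3-week pause defers 3 × 0.333 = 1 woman (1/52 = 1.9%). A 10-working-day pause defers 2 × 0.333 = 0.67.

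**The case against.** The strongest case against is that the trial is not unguarded. IRBs receive every death or injury and can withdraw approval. The PI must evaluate unanticipated effects immediately and must terminate for unreasonable risk. Section 8.5 calls for a site plan whose contents are not visible and which might contain a pause. At one woman per three weeks, hardly anyone is exposed. A site that follows the 24-hour rule also satisfies the 10-day limit.

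Most of this stands, and it limits the point. A reader might infer that the protocol has no stopping provision anywhere, that the DSMB is never told, or that only the PI can halt the trial. Sections 8.4.2 and 8.5.1 contradict the first two, and the provisions on IRB approval contradict the third.

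A reader might also infer that transfusion and fetal or neonatal loss fall outside the termination duty because section 1.3 names bleeding and pregnancy loss as known risks. The documents do not settle this. The section 8.2 definition of an unanticipated surgical effect also covers severity and incidence beyond what the plan identified, so bleeding that needs transfusion may qualify. The opposite argument is open too: the stopping paragraph itself names all four events, so they could be called already identified. The point does not rest on either reading.

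The objection does not remove the core. IRB notice may take up to 10 working days, the power to act on an immediate hazard is not a duty, and notice to the DSMB head is not a review.

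**Conclusion.** The point holds in limited form. Under the stopping label, four events lead only to a report to the PI. Nothing in the visible text of sections 8.2 to 8.5.1 pauses randomisation, or requires DSMB review, after a cerclage-related maternal death or ICU sepsis. For deaths and serious injuries, the 10-day limit conflicts with the 24 hours in section 8.4.1.

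The size is small. It rests on steady accrual of 52 women over 3 years, full use of the 15-working-day limit, and event rates that are assumed because the documents give none. The 0.74 women and 52% that follow from the 10-day limit should not be read as expected exposure, since section 8.2 also says to report immediately and section 8.4.1 requires 24 hours.

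This is a matter of safety governance. The scheduled DSMB review excludes efficacy, and a safety pause involves no efficacy comparison, so it spends no type I error and leaves power and the primary analysis as planned. The conclusion could change if the site safety-monitoring plan already contains a pause.

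**What to change.** Two wording changes, using the existing DSMB:

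1. Under the stopping label in section 8.2, add: *The first maternal death, or maternal sepsis with ICU admission, for which a relation to cerclage cannot be excluded pauses new randomisations until the DSMB has reviewed it (target: within 10 working days) and recommends continuing.* The cannot-be-excluded wording matters because section 8.3 leaves the assessment of association to the investigator. The target keeps the pause from being open-ended.
2. In the same paragraph, replace the 10-day limit with *within 24 hours of the event*, to match section 8.4.1.

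An extension of the evaluation and termination duty in section 8.4.2 is optional. If wanted, word it as *any of the four events listed under Stopping rules*. A phrase such as serious adverse effect would not do, because section 8.2 defines serious injury and leaves that term undefined.

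This is a cheap improvement. A 3-week pause defers about 1 of 52 women, and some may pass the 23 6/7-week limit before it ends. The second change also puts non-serious injuries under the 24-hour limit, which section 8.4.1 now applies only to serious injury, death and unanticipated effects. The optional extension would add PI evaluations and reports of them to the IRB.

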8.3 Recording of Adverse Effects

At each contact with the subject, the investigator must seek information on adverse effects by specific questioning and, as appropriate, by examination. Information on all adverse surgical procedure effects should be recorded immediately in the source document, and also in the appropriate adverse effect module of the case report form (CRF). All clearly related signs, symptoms, and abnormal diagnostic procedures results should be recorded in the source document, though should be grouped under one diagnosis.

All adverse effects occurring during the study period must be recorded. The clinical course of each event should be followed until resolution, stabilization, or until it has been determined that the study treatment or participation is not the cause. Serious adverse effects that are still ongoing at the end of the study period must be followed up to determine the final outcome. Any serious adverse effects that occur after the study period should be recorded and reported promptly (see section 8.3 below).

The minimum initial information to be captured in the subject's source document concerning the adverse effect includes:

- Study identifier
- Subject number
- A description of the event
- Date of onset
- Investigator assessment of the association between the event and study treatment
- Current status
- Whether study treatment was discontinued
- Whether the event is serious and reason for classification as serious

8.4 Reporting of Adverse Effects and Unanticipated Problems

8.4.1 Investigator reporting: Notifying the principal investigator

Principal investigator contact information for reporting purposes

Report adverse effects by phone and facsimile to:

[name]
Email: [contact]
[contact]
[contact]

Adverse Effects

Any adverse effect that results in serious injury or death, and any type of unanticipated adverse effect, regardless of seriousness or severity, must be reported to the principal investigator by telephone within 24 hours of the event.

Within the following 48 hours, the principal investigator shall provide further information, as applicable, on the unanticipated adverse event or the unanticipated problem in the form of a written narrative. This should include a copy of the completed Unanticipated Problem form, and any other diagnostic information that will assist the understanding of the event. Significant new information on ongoing unanticipated adverse effects shall be provided promptly to the principal investigator.

Deviations from the study protocol

Deviations from the protocol must receive both principal investigator and the investigator's IRB approval before they are initiated. Any protocol deviations initiated without principal investigator and the investigator's IRB approval that may affect the scientific soundness of the study, or affect the rights,

safety, or welfare of study subjects, must be reported to the Principal investigator and to the investigator's IRB as soon as a possible, but no later than 5 working days of the protocol deviation.

Withdrawal of IRB approval

An investigator shall report to the principal investigator a withdrawal of approval by the investigator's reviewing IRB as soon as a possible, but no later than 5 working days of the IRB notification of withdrawal of approval.

8.4.2 Investigator reporting: Notifying the IRB

Adverse Effects

All unanticipated effects and all adverse effects resulting in research subject death or injury reported by the investigator to the study Principal investigator must also be reported to the investigator's local IRB in accordance with their reporting requirements, though no later than 10 working days.

Protocol Deviations

Any protocol deviations initiated without principal investigator and/or the investigator's IRB approval that may affect the scientific soundness of the study, or affect the rights, safety, or welfare of study subjects, must be reported to the Principal investigator and to the investigator's IRB as soon as a possible, but no later than 5 working days of the protocol deviation.

Any adverse event that occurs any time during or after the research study, which in the opinion of the principal investigator is:

- Unexpected (An event is "unexpected" when its specificity and severity are not accurately reflected in the protocol-related documents, such as the IRB-approved research protocol, any applicable investigator brochure, and the current IRB-approved informed consent document

AND

- Related to the research procedures (An event is "related to the research procedures" if in the opinion of the principal investigator, the event was more likely than not to be caused by the research procedures.)

The above is required regardless of whether the event is serious or non-serious, on-site or off-site

Adverse Effects

All unanticipated effects and all adverse effects resulting in research subject death or injury must be reported to the investigator's local IRB in accordance with their reporting requirements, though no later than 10 working days.

Protocol Deviations

Any protocol deviations initiated without principal investigator and/or IRB approval that may affect the scientific soundness of the study, or affect the rights, safety, or welfare of study subjects, must be reported to the investigator's IRB as soon as a possible, but no later than 5 working days of the protocol deviation.

Reporting Process

Report unanticipated problems as defined above to the IRB office as a written report of the event (including a description of the event with information regarding its fulfillment of the above criteria, follow-up/resolution and need for revision to consent form and/or other study documentation).

Copies of each report and documentation of IRB notification and receipt will be kept in the Clinical Investigator's study file.

Other Reportable events:

For clinical trials, the following events are also reportable to the IRB:

- Any adverse event that would cause the principal investigator to modify the protocol or informed consent form, or would prompt other action by the IRB to assure protection of human subjects.
- Information that indicates a change to the risks or potential benefits of the research, in terms of severity or frequency. For example:
 - An interim analysis indicates that participants have a lower rate of response to treatment than initially expected.
 - Safety monitoring indicates that a particular side effect is more severe, or more frequent than initially expected.
 - A paper is published from another study that shows that an arm of your research study is of no therapeutic value.
- Breach of confidentiality
- Change to the protocol taken without prior IRB review to eliminate apparent immediate hazard to a research participant.
- Incarceration of a participant when the research was not previously approved under Subpart C and the investigator believes it is in the best interest of the subject to remain on the study.
- Complaint of a participant when the complaint indicates unexpected risks or the complaint cannot be resolved by the research team.
- Protocol violation (meaning an accidental or unintentional deviation from the IRB approved protocol) that in the opinion of the investigator placed one or more participants at increased risk, or affects the rights or welfare of subjects.

Unanticipated Adverse Effects

Evaluation

The principal investigator shall immediately evaluate each Unanticipated Adverse Effect. Such evaluations shall be reported to the IRB office, and participating investigators, within 10 working days after the principal investigator first receives notice of the effect.

Unreasonable risk to subjects

After evaluating an Unanticipated Adverse Effect, if the principal investigator determines the effect presents an unreasonable risk to subjects, the principal investigator shall terminate the study or parts of the study presenting that risk as soon as possible. Study termination shall occur no later than 5 working days after the principal investigator makes this determination and not later than 15 working days after the principal investigator first received notice of the effect.

Withdrawal of IRB approval

The Principal investigator shall notify the IRB office and participating investigators of any withdrawal of approval of the study by a reviewing IRB within 5 working days after receipt of the withdrawal of approval.

